4.5.1.1.3 Risk of TLS with Alvocidib and Guidelines for Management

TLS management during treatment with alvocidib was implemented in previous studies, which included medical prophylaxis for hyperuricemia, as well as aggressive monitoring and management of hyperkalemia and other biochemical laboratory abnormalities. Rapid development of hyperkalemia has been of particular concern in earlier studies with the hybrid dosing regimen of alvocidib. While these guidelines are not necessarily consistent with specific standard recommendations for the treatment of TLS, they are recommended based on previous experience with the treatment of patients with the hybrid dosing regimen of alvocidib. These measures resulted in a lower incidence of TLS without adverse outcomes.

For this reason, Investigators are encouraged to follow the recommended guidelines below but may follow your own institution's protocols in determining the best treatment for your patients.

- If potassium levels are increasing to >4.0 mEq/L, patients should receive a 30 gm dose of sodium polystyrene sulfonate, unless there are other likely causes of hyperkalemia other than TLS or contraindication to its use.
- If potassium levels rise to >5.0 mEq/L, in addition to the 30-gm dose of sodium polystyrene sulfonate, patients should also receive 10 units of IV rapid-acting insulin and 25 gm (1 ampule) of IV dextrose 50%, unless there are other likely causes of hyperkalemia other than TLS or contraindication to its use. Investigators are strongly encouraged to consider patient hospitalization for inpatient monitoring and follow up.
- If potassium levels rise to >5.5 mEq/L, patients should be considered for emergent intermittent or continuous dialysis.
- Calcium supplementation should only be given for symptomatic hypocalcemia in this setting to avoid renal precipitation of calcium phosphate crystals.
- Patients who develop clinical evidence of cytokine release syndrome or who have hyperkalemia requiring dialysis will receive immediate steroid therapy with an equivalent of at least 20 mg of IV dexamethasone.

4.5.1.2 Diarrhea

Alvocidib can induce diarrhea when given over a short period of time. Dehydration from diarrhea can exacerbate the morbidity associated with tumor lysis syndrome (ie, acute renal failure). Over-the-counter measures are typically effective in this setting if initiated early. It is strongly suggested that patients take 2 tablets of loperamide, 2 mg each (or equivalent), prior to the alvocidib IVI and then take 1 tablet (2 mg) for every loose stool up to a maximum of 8 tablets (16 mg) in a 24-hour period. The diarrhea observed with alvocidib almost always resolves following completion of therapy, so treatment with loperamide following completion of therapy will not be required in most patients. If loperamide (or equivalent) does not control diarrhea, diphenoxylate hydrochloride with atropine sulfate (or equivalent) 5 mg orally four (4) times daily may be added. If diarrhea is not controlled with the above prophylactic regimens and is grade 2 or greater, patients should contact the clinic and study drug treatment should be held until diarrhea has resolved. Should diarrhea persist beyond Cycle 1, patients should undergo testing for *C. difficile*. Should testing indicate the presence of *C. difficile*, appropriate antibiotics targeting this infection should be initiated. Should testing exclude the presence of *C. difficile*, diarrhea prophylaxis similar to Cycle 1 should be continued in subsequent cycles. Replacement of excessive fluid losses should be done unless otherwise clinically indicated.

4.5.1.3 Nausea/Vomiting

Antiemetics (ie, 5-hydroxytryptamine [5-HT3] receptor inhibitor or other antiemetic medications) are permitted according to standard practices at each investigational site.

4.5.1.4 Infection Prevention

Prophylactic antibiotic, antiviral, and/or antifungal therapy is left to the discretion of the treating physician and according to institutional standards.

Routine growth factor support is not allowed before achieving a leukemia-free bone marrow state. Support with growth factors (eg, filgrastim) is discouraged. If a patient has Grade 4 sepsis with life-threatening infection with ongoing neutropenia, then this may be considered at the discretion of the Investigator.

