11. Female patients of childbearing potential who are sexually active and unwilling to use a medically acceptable method of contraception associated with a low failure rate during and for at least 6 months after the last dose of study drug. (Patients will be considered to be of childbearing potential unless surgically sterilized by hysterectomy, or bilateral tubal ligation/salpingectomy, or postmenopausal for at least 2 years.)
12. Male patients with partners of childbearing potential who are unwilling to use condoms in combination with a second effective method of contraception during the trial and for at least 6 months after the last administration of study treatment.
13. Patients who are inappropriate for participation in the study for other reasons in the opinion of the investigator or sub-investigator(s)
14. Patients with a known hypersensitivity to **DEC (those patients enrolled in dose escalation)**, AZA, or mannitol
- 15. Patients who have received erythropoietin-stimulating agents (ESAs) within 2 weeks (14 days) prior to Cycle 1/Day 1**

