4.6.2 Concomitant Therapies

Concomitant therapies are any new or existing medications or therapy taken by the patient including:

- Drugs, including but not limited to, prescription, over-the-counter, birth control pills/patches/hormonal devices, and homeopathic preparations
- Nondrug therapies, including but not limited to, thermal/laser/radiation procedures, vitamins, herbal medicines/supplements.

During the Screening process (up to 28 days prior to anticipated first dose of study drug), information on all concomitant therapies, medications, and procedures will be recorded in the source documents and appropriate CRF along with the diagnosis or reason for use.

Once the patient receives the first dose of study drug, recording of concomitant therapies will be limited to any new medication or modification of an existing medication taken for treatment of an adverse event (AE). These therapies will be recorded in the source documents and appropriate CRF along with the diagnosis or reason for use. Those therapies used for the treatment of an adverse event are to be linked to an AE and documentation of the AE must also be completed (refer to [Section 8](#)).

If a branded product is being taken, the generic name should be reported, if known.

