4.6.2.2 Prohibited Therapies

The following medications are excluded from concomitant use:

- Antileukemic therapy (chemotherapy, radiation therapy, immunotherapy) within the last 3 weeks prior to the first study drug administration and during the cycle of study treatment.
- Live vaccines within 14 days prior to first study drug administration, during the study, and for approximately 3 months after the last dose of study drug.
- ***Routine growth factor support is not allowed. Growth factor support can be given at the discretion of the Investigator and with the Medical Monitor's approval in the presence of life-threatening infection with ongoing neutropenia.***

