APPENDIX F – INTERNATIONAL WORKING GROUP (IWG) RESPONSE CRITERIA (2006) (CONT)

Hematologic improvement*	Response criteria (responses must last at least 8 wk)†
Erythroid response (pretreatment, < 11 g/dL)	Hgb increase by ≥ 1.5 g/dL Relevant reduction of units of RBC transfusions by an absolute number of at least 4 RBC transfusions/8 wk compared with the pretreatment transfusion number in the previous 8 wk. Only RBC transfusions given for a Hgb of ≤ 9.0 g/dL pretreatment will count in the RBC transfusion response evaluation†
Platelet response (pretreatment, $< 100 \times 10^9/L$)	Absolute increase of $\geq 30 \times 10^9/L$ for patients starting with $> 20 \times 10^9/L$ platelets Increase from $< 20 \times 10^9/L$ to $> 20 \times 10^9/L$ and by at least 100%†
Neutrophil response (pretreatment, $< 1.0 \times 10^9/L$)	At least 100% increase and an absolute increase $> 0.5 \times 10^9/L$ †
Progression or relapse after HI‡	At least 1 of the following: At least 50% decrement from maximum response levels in granulocytes or platelets Reduction in Hgb by ≥ 1.5 g/dL Transfusion dependence

Deletions to the IWG response criteria are not shown.

To convert hemoglobin levels from grams per deciliter to grams per liter, multiply grams per deciliter by 10.

Hgb indicates hemoglobin; RBC: red blood cell; HI: hematologic improvement.

*Pretreatment counts averages of at least 2 measurements (not influenced by transfusions) ≥ 1 week apart (modification).

†Modification to IWG response criteria.

‡In the absence of another explanation, such as acute infection, repeated courses of chemotherapy (modification), gastrointestinal bleeding, hemolysis, and so forth. It is recommended that the 2 kinds of erythroid and platelet responses be reported overall as well as by the individual response pattern.

[28]

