## **10.2 Protocol Violations or Deviations**

Protocol deviations were not collected per the eCRFs.

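### The growth-factor rules conflict between protocol sections, and the erythroid criterion that scores hematologic improvement omits the no-ESA condition set in the objectives

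*Protocol*

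**What the plan says.** **Growth factors.** Protocol 4.5.1.4 reads "Routine growth factor support is not allowed before achieving a leukemia-free bone marrow state". It then discourages such support and, for Grade 4 sepsis with neutropenia, says "then this may be considered at the discretion of the Investigator". Section 4.6.2.2, like the supportive-care text in the Synopsis, bars routine support outright. Its exception is a life-threatening infection in a neutropenic patient: "Growth factor support can be given at the discretion of the Investigator and with the Medical Monitor's approval".

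**ESAs.** Exclusion criterion 15 covers "Patients who have received erythropoietin-stimulating agents (ESAs) within 2 weeks (14 days) prior to Cycle 1/Day 1". The on-study list in 4.6.2.2 does not name ESAs. The transfusion and hemoglobin objectives (Protocol 3.1 and 3.2; SAP 3.2 and 3.5) credit the 1.5 g/dL rise only when it is achieved without an ESA.

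**Scoring.** Protocol 11.9 counts HI in CRR, and 11.2 counts it in both stages of the Simon design. HI is scored by Appendix F. The erythroid limb there asks for the same 1.5 g/dL rise but does not mention ESAs. The neutrophil limb asks for "At least 100% increase and an absolute increase" above a fixed amount, with no growth-factor condition. Every HI response must last at least 8 weeks.

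**Recording.** Protocol 4.6.2 says that after the first dose "recording of concomitant therapies will be limited to any new medication or modification of an existing medication taken for treatment of an adverse event". The opening of 4.5, and 4.6.2.1, require concomitant medication to be entered on the case report form.

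**The concern.** HI alone makes a patient a responder under the protocol's definition. If support that raises counts is permitted on one reading of the plan, and the scoring criterion does not exclude it, an effect of that support can be credited to the alvocidib regimen. The erythroid limb is the clearest case. The plan already recognises the problem, because its objectives carry the no-ESA condition, but the condition is missing where responses are scored. Protocol 1.2 itself lists erythropoiesis-stimulating agents among supportive care for MDS, so their use in this population is foreseeable.

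Two things would be at stake. One is whether a scored response reflects the study regimen. The other is whether a reader of the report could tell a supported count from an unsupported one.

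**Working it through.** **1. The growth-factor rules side by side.**

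| Feature | 4.5.1.4 | 4.6.2.2 and Synopsis |
|---|---|---|
| Time limit of the ban | Until a leukemia-free marrow | None |
| Trigger for the exception | Grade 4 sepsis, life-threatening, with neutropenia | Life-threatening infection with neutropenia |
| Who decides | Investigator | Investigator with Medical Monitor approval |

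The texts differ on all three features. The marrow state that ends the ban in 4.5.1.4 is not a category in Appendix F.

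**2. The erythroid condition.** Objectives: a rise of at least 1.5 g/dL, no ESA. Appendix F: a rise of at least 1.5 g/dL from a pretreatment value below 11 g/dL, held for 8 weeks, with no ESA condition. Example: hemoglobin going from 8.5 to 10.0 g/dL on an ESA is a rise of 10.0 − 8.5 = 1.5 g/dL. If it lasts 8 weeks, Appendix F is met and the objective is not.

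**3. The plan's Phase 2 figure.** Inputs from Protocol 11.2: stop if there is at most 1 response in 15; positive if there are at least 6 in 25; null rate 10%; alternative 30%. With X1 ~ Bin(15, p) and X2 ~ Bin(10, p),

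P(positive) = Σ over x = 2,…,15 of P(X1 = x) · P(X2 ≥ 6 − x).

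At p = 0.10 this is 0.0328, with probability 0.549 of stopping after Stage 1. At p = 0.30 it is 0.8017. A search over designs with error at most 0.05 and power at least 80% returns this same design, so it reproduces. The stated 0.05 is the design limit; the attained error is 0.033.

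**4. Sensitivity to misclassification.** Let q be the share of true non-responders scored as HI because of an ESA or growth factor. The documents give no value, so q is an assumption. The effective null rate is 0.10 + 0.90q; for example 0.10 + 0.90 × 0.05 = 0.145.

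| q (assumed) | Effective null rate | P(pass Stage 1) | P(positive) |
|---|---|---|---|
| 0 | 0.100 | 0.451 | 0.033 |
| 2% | 0.118 | 0.543 | 0.065 |
| 5% | 0.145 | 0.662 | 0.141 |
| 10% | 0.190 | 0.809 | 0.331 |
| 20% | 0.280 | 0.951 | 0.736 |

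P(positive) passes 0.05 once q exceeds about 1.2% (effective null rate about 11.1%).

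**5. Could the use be found afterwards?** Partly. Protocol 8.4 makes a laboratory abnormality an adverse event when it needs treatment, and 4.6.2 then requires the drug to be recorded. Sections 4.5 and 4.6.2.1 ask for recording without the adverse-event limit, so they are in tension with 4.6.2. Support continued for a cytopenia already present at baseline is the case the sections do not settle. A breach would not surface as a deviation in the study database, since SAP 10.2 states "Protocol deviations were not collected per the eCRFs". SAP 10.6 gives concomitant drugs in listings only, although Protocol 11.7 plans a tabulation.

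**The case against.** A reader might infer that any count rise on a growth factor or ESA is a response, that such use is open on study and would go unseen, and that the Phase 2 error rate is therefore compromised. The documents do not support that reading.

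- Appendix F sets thresholds that must hold for 8 weeks, so a short course during sepsis would not qualify unless the rise lasted. Protocol 6.2 also has patients without a response after Cycle 2 considered for removal.
- Section 4.6.2.1 permits only medication that does not interfere with study assessments, which can be read to exclude an ESA when hemoglobin is assessed. The general ban in 4.6.2.2 is not limited to myeloid factors. The gap is an undefined term, not an open permission.
- The route left by 4.5.1.4 opens only after a leukemia-free marrow. A patient with excess blasts who gets there will usually meet marrow CR and already count. A move from marrow CR to CR changes neither CRR nor the Simon count. Patients with low baseline blasts are the exception.
- Sections 4.5, 4.6.2.1 and 8.4 would capture much of the use.
- The SAP supersedes the protocol's statistics, has no HI category in best response, lists HI by patient (section 11), plans no inference and records zero Phase 2 patients.

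All of this stands, and it narrows the point. It does not remove the three-way conflict between the growth-factor texts, or the absence from the scoring criterion of a condition the objectives impose.

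**Conclusion.** The point holds in a limited form. The growth-factor texts contradict each other on time limit, trigger and approver. The plan does not say whether ESAs are covered after the first dose. The erythroid criterion feeding HI, CRR and the Simon count omits the objectives' no-ESA condition, so a qualifying rise sustained for 8 weeks on an ESA is a response as written.

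The rise from 3.3% to 14.1% or 33.1% is an illustration. It rests entirely on assumed misclassification of 5% or 10% of non-responders and on a true rate of 10%. It describes the protocol's design, not a realised error or an analysis that will be run.

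The present relevance is to the 20 Phase 1b patients. CRR including HI is a Phase 1b secondary objective (SAP 3.2). Best response is tabulated, and its CR category depends on hemoglobin, platelet and neutrophil floors that carry no growth-factor condition. HI is listed by patient, and the correlation in SAP 14 uses responses that include HI. This is worth correcting, but the documents do not show that any response was misclassified.

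**What to change.** 1. Reconcile Protocol 4.5.1.4, 4.6.2.2 and the Synopsis into one statement on growth factors, and say whether the term includes ESAs. Which rule applies is for the sponsor's clinical team.
2. Carry the objectives' no-ESA condition for the hemoglobin rise into Protocol 11.9, a study note to Appendix F, and SAP 11.
3. In the same places, flag any HI or CR whose counts were reached during growth-factor use. A flag is enough: a blanket rule refusing credit for every neutrophil or platelet response would go beyond the plan's own text.
4. Reconcile the adverse-event limit in 4.6.2 with 4.5 and 4.6.2.1, so that all growth-factor and ESA use is recorded with dates.
5. In SAP 10.6, list or tabulate that use by cohort beside the response data. With the study closed, do this from the data held and state that capture may be incomplete.

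The cost is wording, one drug class that is always recorded on the existing form, and one small table or listing. The downside is that CRR may be slightly lower.

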4.5.2 Management of Hematologic Toxicities

Bone marrow suppression and associated complications are expected events during MDS therapy and are part of the treatment process (marrow emptying of abnormal cells). Therefore, hospitalization or prolongation of hospitalization for myelosuppression and associated complications directly related to the myelosuppression, such as fever, infections and bleeding, will not be reported as serious adverse events (SAEs), but will be reported as adverse events on the adverse event case report form and will be summarized in the updated and final reports.

4.5.3 Dose-limiting Toxicities

Dose-limiting toxicities (DLTs) will be determined during Cycle 1 and defined as follows based on the NCI CTCAE v5.0:

- Any Grade 5 toxicity that is not clearly and incontrovertibly related to the underlying disease or extraneous causes
- Any Grade 4 nonhematologic toxicity considered at least possibly drug related
- Grade 4 neutropenia lasting ≥ 42 days from the start of a cycle in the absence of evidence of active disease
- Any AST or ALT elevation $\geq 3 \times$ ULN accompanied by serum bilirubin levels $> 2 \times$ ULN
- Any Grade 3 nonhematologic toxicity considered at least possibly drug related and that does not resolve to \leq Grade 2 within 48 hours, with the following exceptions:
 - Grade 3 bilirubin, AST, ALT or alkaline phosphatase will be considered dose-limiting only if resolution to \leq Grade 2 requires more than 7 days

- Grade 3 diarrhea, mucositis, nausea, or vomiting will be considered dose limiting only if resolution to \leq Grade 2 (including use of supportive care) requires more than 7 days
- \geq Grade 3 creatinine elevation that does not resolve to \leq Grade 2 within 7 days
- Anorexia, fever, neutropenic fever, and infections of any grade
- Bone marrow hypoplasia that occurs for >42 days with bone marrow (BM) cellularity $\leq 5\%$ and no evidence of MDS/leukemia. Bone marrow disease assessments conducted per protocol on Day 28 (± 3 days) of every even cycle may be used to guide this decision.

4.5.4 Dose Modifications

Doses of DEC, AZA, and alvocidib will not be reduced during Cycle 1. In patients who receive multiple treatment cycles, the alvocidib dose may be reduced by one dose level based on the observed toxicity that occurred during the preceding cycle. If further toxicities occur during one or more cycles at the new reduced dose level, no further reductions will be permitted, and the patient should be discontinued from the study.

No dose re-escalations will be allowed for any patient who had a previous dose reduction due to toxicity or delayed recovery.

In the event of toxicity in Cycles 2+, the dose of DEC or AZA may be adjusted according to the guidelines set forth in the US Prescribing Information (USPI) for each drug [29, 30]. Guidelines for dose adjustments of alvocidib are provided in [Table 7](#).

Table 7: Guide to Alvocidib Dose Adjustments Based on Toxicities

Drug-related AE Grade	Action Regarding Alvocidib Dosage
Grade 1	Current dose level
Grade 2	Investigator's option to reduce dose by 1 dose level with agreement of the Medical Monitor
Grade 3*	Withhold, then reduce dose by 1 dose level upon recovery to \leq Grade 1 or baseline with agreement of the Medical Monitor.
Grade 4	Investigator and Medical Monitor review to determine if patient may continue on study with appropriate dose reduction upon recovery to \leq Grade 1 or baseline.

* Excluding brief (based on the investigator's judgment) Grade 3 vomiting or diarrhea with suboptimal management. In addition, Grade 3 toxicities must also meet the definition of a DLT.

Patients who experience a DLT will be required to discontinue study participation, unless the Investigators and Medical Monitor determine that it is in the best interest of the patient to continue with the dose reduction and only upon recovery of the toxicity to Grade 2 or better.

Dose reduction will be required for patients who have a delay in treatment greater than 6 weeks due to a lack of recovery of any hematologic or nonhematologic toxicity, even if DLT criteria are not met. Subsequent retreatment of patients who are not able to be treated after a 6-week delay and who eventually recover will be discussed between Investigators and Medical Monitor considering the potential benefit/risk for the individual patient. In addition, dose reductions may be permitted for patients who have toxicities that do not meet the criteria of a DLT. These toxicities will be discussed by the Investigators and Medical Monitor to determine if it would be in the best interest of the patient to continue to receive decitabine **or azacitidine** and a reduced dose of alvocidib.

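### Section 4.5.4 gives two different recovery conditions for resuming reduced-dose alvocidib after the same Grade 3 or Grade 4 dose-limiting toxicity

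*Protocol*

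**What the plan says.** All the conflicting text is in Protocol Section 4.5.4.

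- **Table 7, Grade 3 row.** The action is "Withhold, then reduce dose by 1 dose level upon recovery to" Grade 1 or lower, or baseline. The rest of the cell reads "Grade 1 or baseline with agreement of the Medical Monitor".
- **Footnote to that row.** It excludes brief, suboptimally managed vomiting or diarrhea, then adds "In addition, Grade 3 toxicities must also meet the definition of a DLT".
- **Table 7, Grade 4 row.** The action is "Investigator and Medical Monitor review to determine if patient may continue on study with appropriate dose reduction upon recovery to" the same level, Grade 1 or lower or baseline.
- **Paragraph directly below the table.** "Patients who experience a DLT will be required to discontinue study participation, unless the Investigators and Medical Monitor determine" that continuing with the dose reduction is in the patient's best interest, and then "only upon recovery of the toxicity to Grade 2 or better".

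The section also bars reductions in Cycle 1 and bases later reductions on toxicity in the cycle just completed. Its last paragraph, on treatment delays and on toxicities short of a DLT, names no recovery grade. The SAP repeats the DLT definition in Section 8.6 and gives no recovery rule.

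**The concern.** Both rules decide when a patient may receive alvocidib again at a reduced dose, and for some patients they give opposite answers. An investigator following the table would wait; one following the paragraph could re-treat. What is at stake is first the patient's residual toxicity at the next dose. Second, Protocol Section 4.2 and SAP Section 12 say that toxicity in Cycle 2 and later is considered when the RP2D is set. Toxicity seen after re-treatment at Grade 2 is not the same evidence as toxicity seen after recovery to Grade 1 or lower.

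**Working it through.** No sample size, power or error rate is involved, so the check compares the texts.

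**Step 1: which events each rule covers.** The Grade 3 row covers drug-related Grade 3 events that, by its footnote, meet the DLT definition. The Grade 4 row covers drug-related Grade 4 events. The paragraph covers every patient with a DLT, whatever the grade.

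**Step 2: whether the sets overlap.** Section 4.5.3 lists as a DLT "Any Grade 3 nonhematologic toxicity considered at least possibly drug related and that does not resolve to" Grade 2 or lower within 48 hours, with stated exceptions. It also lists Grade 4 nonhematologic toxicity judged at least possibly related. Grade 3 and Grade 4 DLTs therefore fall under both a table row and the paragraph.

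**Step 3: compare the conditions within the overlap** (assuming baseline below Grade 3).

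| Residual grade at decision | Baseline grade | Table 7 met? | DLT paragraph met? | Result |
|---|---|---|---|---|
| 0 or 1 | any | yes | yes | agree |
| 2 | 2 | yes, through the baseline clause | yes | agree |
| 2 | 0 or 1 | no | yes | **conflict** |
| 3 or higher | 0 to 2 | no | no | agree |

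Only one cell conflicts. The gap there is Grade 2 (allowed by the paragraph) minus Grade 1 (the highest level the table allows when baseline is below Grade 2): 2 − 1 = 1 CTCAE grade.

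**Step 4: look for a reading that separates the rules.**

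- *The table is for events that are not DLTs.* The footnote to the Grade 3 row says the opposite, and reductions for toxicities short of a DLT are handled separately at the end of the section.
- *The paragraph governs staying on study and the table governs dosing.* The paragraph ties continuing to the dose reduction, and the Grade 4 row itself speaks of remaining on study.
- *The paragraph is for Cycle 1 and the table for later cycles.* Because reductions follow toxicity in the preceding cycle, a Cycle 1 DLT leads to a Cycle 2 decision to which both rules apply.

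None of the three separates them.

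**The case against.** The strongest defence is that the paragraph states a necessary condition, so anyone who meets the tighter of the two levels complies with both rules. That is true, and it makes this a case of ambiguity in which joint compliance remains possible. But the text does not say the rules are cumulative. If they were, the paragraph's level would never be the binding one for a Grade 3 or Grade 4 event.

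A second defence is that the Medical Monitor takes part in each route: the Grade 3 row, the Grade 4 row and the DLT paragraph. Table 7 is also titled as a guide. This stands as a limit. A reader might infer that sites will re-treat differently; the documents support only that they could. A common decision-maker may reduce variation but does not supply the missing criterion.

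A third is timing. Section 4.5.3 says DLTs are determined in Cycle 1, and later events are described elsewhere as adverse events meeting the DLT definition. On that wording the paragraph may reach only Cycle 1 events. This too stands: the conflict is clearest at the Cycle 1 to Cycle 2 decision and less certain afterwards.

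Stronger readings that the documents do not support:

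- *Every patient who continues after a DLT is affected.* The table in the working shows agreement in all but one situation.
- *A quarter to a third of a cohort is affected.* That puts one hypothetical patient over the cohort sizes of 3 or 4 at closure (SAP Section 1). The documents report no patient re-treated after a DLT.
- *Dose-intensity comparisons are compromised.* Protocol Section 11.8 mentions dose intensity, but SAP Section 10.7 summarises exposure by cycles completed and weeks on study, and the SAP states that it supersedes the protocol's statistical section.

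**Conclusion.** The point holds in a narrow form. Section 4.5.4 sets two recovery levels for the same Grade 3 or Grade 4 DLT and states no precedence. They conflict only when the event has improved to Grade 2 and baseline was below Grade 2. The size is one CTCAE grade of residual toxicity at re-treatment; how often this would arise cannot be estimated from the documents.

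The consequence is for patient safety and for interpreting the later-cycle toxicity considered for the RP2D, for which no formula is given. The MTD rule rests on Cycle 1 DLTs, and no dose is reduced in Cycle 1, so it is untouched. The Simon two-stage figures do not depend on it either.

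The conclusion assumes that the Table 7 footnote means what it says, namely that the Grade 3 row is confined to events meeting the DLT definition. The SAP records closure with 20 patients in Phase 1b and none in Expansion or Phase 2, so for those later parts the point concerns the design as written.

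**What to change.** Reconcile Table 7, its footnote and the DLT paragraph in Section 4.5.4 so that one recovery criterion applies to each situation, and state which text governs when an event falls under both. Say whether the same criterion applies to events meeting the DLT definition in Cycle 2 and later. The choice of threshold belongs to the sponsor and its clinical advisers; no view is offered here.

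The cost is a few sentences, with no change to sample size, the dose-escalation rule or the analyses. For the closed study, the synoptic report could state whether any patient was re-treated after a DLT and at what residual grade. SAP Section 10.2 says protocol deviations were not collected on the eCRFs, so inconsistent use of the two rules would not appear there as deviations.
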